7.1.2.2 Weeks 4, 6, 8 (\pm 7 Days) – for all Subjects

- Vital signs: sitting blood pressure (BP), heart rate (HR)
- AEs/ADEs/SAEs
- Concomitant medications
- Blood draw for fasting lipids (\geq 9 hour fasting sample), ApoA1, ApoB, Lp(a), PK (AMG 145) and PCSK9.
- Administer IP to subjects (At week 6 IP administered only for Q2W subjects).

7.1.2.3 Week -1, and Week 9 (\pm 2 Days) – for Apheresis Subjects Only

- Vital signs: sitting blood pressure (BP), heart rate (HR)
- AEs/ADEs/SAEs
- Concomitant medications
- Blood draw for fasting lipids (\geq 9 hour fasting sample), ApoA1, ApoB, PK, Lp(a), AMG 145 (week 9 only), PCSK9, and serum pregnancy (females of childbearing potential only) and FSH (only if required to ensure menopause in a female subject [see [exclusion criterion 4.2.18](#)]) by central laboratory (for week -1)

7.1.2.4 Interval Visits – All Subjects (Weeks 16 and 20 \pm 7 Days)

- Vital signs: sitting blood pressure (BP), heart rate (HR)
- AEs/ADEs/SAEs
- Blood draw for fasting lipids (\geq 9 hour fasting sample), ApoA1, ApoB, Lp(a), PK (AMG 145) and PCSK9
- Concomitant medications
- Administer IP to subjects.

7.1.2.5 Quarterly Visits - All Subjects (Week 12, 24, 36, etc \pm 7 Days)

- Vital signs: sitting blood pressure (BP), heart rate (HR)
- Measurement of height, weight, and Tanner stage should be performed every 48 weeks for adolescent subjects (see the [study glossary](#) for definition of adolescence and [Appendix E](#) for guidance on Tanner staging)
- AEs/ADEs/SAEs
- Concomitant medications
- Blood draw for serum pregnancy (performed every 6 months for females of childbearing potential only) – **Additional pregnancy testing may be performed at the discretion of the investigator**
- Blood draw for fasting lipids (\geq 9 hour fasting sample), ApoA1, ApoB, chemistry, hematology, PK (AMG 145), PCSK9, coagulation, hsCRP, Lp(a), HbA1c, and anti-AMG 145 antibodies
- Blood draw for biomarkers at week 12 only
- Fasting Vitamin E at weeks 12, 24, 48 (year 1), 72, and 96 (year 2)
- Administer IP to subjects. – Please note starting at week 24 subjects will receive a 12 week supply of IP to be self-administered every 2 to 4 weeks, as applicable

7.1.2.6 End of Study (Week 260)/Early Term OL Visit – All Subjects

- Vital signs: sitting blood pressure (BP), heart rate (HR)
- AEs/ADEs/SAEs
- Concomitant medications
- Physical exam
- Measurement of, height, weight, and Tanner stage for adolescent subjects (see the [study glossary](#) for definition of adolescence and [Appendix E](#) for guidance on Tanner staging)
- Body weight
- Blood draw for serum pregnancy (for females of childbearing potential only)
- Blood draw for fasting lipids (≥ 9 hour fasting sample), ApoA1, ApoB, chemistry, hematology, PK (AMG 145), PCSK9, coagulation, hsCRP, Lp(a), HbA1c, fasting Vitamin E, and anti-AMG 145 antibodies
- Urinalysis
- 12 Lead ECG in triplicate using centralized ECG services equipment

7.1.3 Standardization of Study Procedures

7.1.3.1 Measurement of Vital Signs

Blood pressure (BP) and heart rate (HR) should be measured at each visit. BP should continue to be measured in the same arm as in the parent study unless a concomitant condition favors the use of a different arm. The appropriate size cuff should be used. The diastolic blood pressure (DBP) will be recorded as the pressure noted when sound disappears (Korotkoff Phase V). Blood pressure and heart rate measurements should be determined after the subject has been seated for at least 5 minutes. The subject's pulse should be measured for 30 seconds and the number should be multiplied by 2 to obtain heart rate.

7.1.3.2 Blood Sample Use

Any blood sample collected according to the Schedule of Assessments ([Appendix A](#)) may be analyzed for any of the tests outlined in the protocol and for any tests necessary to ensure subject safety. This includes testing to ensure analytical methods produce reliable and valid data throughout the course of the study. This may also include, but is not limited to, investigation of unexpected results, incurred sample reanalysis, and analyses for method transfer and comparability.

Amgen may do additional testing on the remaining samples (ie, residual and back-up) to investigate and better understand hypercholesterolemia metabolic disorders, the dose response and/or prediction of response to AMG 145, characterize antibody response,

and characterize aspects of the molecule (eg, metabolites). Results from this analysis will be documented and maintained, but may not be reported as part of this study.

7.1.3.3 Lipid Measurements

Investigators and staff involved with this trial should remain blinded to locally obtained lipid panels until the week 8 visit for all subjects that transition from an ongoing blinded (or blinded portion) parent study into this study, in order to avoid potential unblinding of the ongoing parent study.

If a lipid panel is drawn during the first 8 weeks, all reasonable steps must be undertaken to avoid informing the subject and study personnel of the results.

7.1.3.4 Laboratory Assessments

All on-study laboratory samples will be processed and sent to the central laboratory. Amgen or designee will be responsible for PK (AMG 145 and PCSK9 serum levels), anti-AMG 145 antibody, and biomarker development assessments and the central laboratory will ship the samples to Amgen or a specialty laboratory for assay (depending on the assessment).

The central laboratory will provide a study manual that outlines handling, labeling, and shipping procedures for all blood samples. The date and time of sample collection will be recorded in the source documents at the site.

[Table 3](#) below outlines the specific analytes for serum chemistry, hematology, urinalysis, and other testing to be conducted.

Table 3. Analyte Listing

Chemistry	Coagulation	Urinalysis	Hematology	Other Labs
Sodium	PT/INR	Specific gravity	Hemoglobin	Fasting lipids
Potassium		pH	Hematocrit	• Total cholesterol
Chloride		Blood	MCV	• HDL-C
Bicarbonate		Protein	MCH	• LDL-C
Total protein		Glucose	MCHC	• Triglycerides
Albumin		Bilirubin	RDW	• VLDL
Calcium		WBC	Platelets	• Non-HDL-C
Magnesium		RBC	RBC	ApoA1
Phosphorus		Epithelial cells	WBC	ApoB
Glucose		Bacteria	Differential	ApoB/ApoA1 ratio
BUN or Urea		Casts	• Neutrophils	Total Cholesterol/HDL-C
Creatinine		Crystals	• Bands	hsCRP
Uric acid			• Eosinophils	Lp(a)
Total bilirubin			• Basophils	Anti-AMG 145 antibodies
Direct bilirubin			• Lymphocytes	AMG 145 (PK)
CK			• Monocytes	PCSK9
ALP				HbA1c
LDH				FSH
AST (SGOT)				Fasting Vitamin E
ALT (SGPT)				eGFR (calculated)
				Serum HcG

Central laboratory results of the lipid panel, ApoA1, ApoB, Lp(a), and hsCRP will not be reported to the investigator prior to week 8 for subjects coming from a blinded (or blinded portion) of a parent study, since some laboratory results may inadvertently unblind investigators to treatment assignment in the parent study. Subjects coming from a blinded (or blinded portion) parent study will have AMG 145 and PCSK9 levels blinded until week 4 since some laboratory results may inadvertently unblind investigators to treatment assignment in the parent study. Vitamin E samples will be blinded to investigators and subjects in the first 96 weeks of the study. Investigators should not perform local testing of these analytes during this time.

7.1.3.5 Tanner Staging (Sexual Maturity Ratings)

Tanner staging is widely used to assess physical development during puberty in 5 stages (from preadolescent to adult). Also known as Sexual Maturity Ratings (SMRs), Tanner stages are a way of assessing the degree of maturation of secondary sexual characteristics (see [Appendix E](#) for guidance). The developmental stages of the adolescent's sexual characteristics will be rated and recorded separately (ie, one stage for pubic hair and one for breasts in females, one stage for pubic hair and one for

genitals in males), because these characteristics may differ in their degree of maturity. For adolescent subjects (as defined in the study glossary), Tanner staging should continue to be performed yearly (every 48 weeks) throughout the study. If Tanner staging cannot be performed on Study Day 1, it should be performed at the next scheduled study visit (along with height and weight), and then every 48 weeks starting at the week 48 visit.

For adolescent subjects, in addition to prospective assessments of Tanner stage, height, and weight, historical assessments (ie, including pre-study measurements) will be recorded. Measurements of, height, weight and Tanner stage made at age 8 years or older that are recorded in the patient's chart should be documented in the appropriate eCRF(s).

7.2 Antibody Testing Procedures

Blood samples will be collected quarterly during the first year and yearly thereafter from all subjects for the measurement of anti-AMG 145 binding antibodies. All subjects who have received at least 1 administration of AMG 145 will have samples assayed for binding and, if positive, neutralizing antibodies. Samples testing positive for binding antibodies will also be tested for neutralizing antibodies and may be further characterized for quantity/titer, isotype, affinity, and presence of immune complexes. Sites will be notified of any positive neutralizing antibody results to AMG 145. If results are not provided, no neutralizing antibodies to AMG 145 have been detected. Additional blood samples may be obtained to rule out anti-AMG 145 antibodies during the study. Subjects who test positive for neutralizing antibodies to AMG 145 at the final scheduled study visit will be asked to return for additional follow-up testing. This testing should occur approximately every 3 months starting from when the site has been notified of the positive result, until: (1) neutralizing antibodies are no longer detectable or (2) the subject has been followed for a period of at least 1 year (\pm 4 weeks). More frequent testing (eg, every month) or testing for a longer period of time may be requested in the event of safety-related concerns. Follow-up testing will not be required where it is established that the subject did not receive AMG 145. All follow-up results, both positive and negative will be communicated to the sites.

7.3 Pharmacokinetic Sampling

7.3.1 All Subjects

Blood samples will be collected as shown in the Schedule of Assessments ([Appendix A](#)) to determine pre-dose AMG 145 and fasting PCSK9 serum concentration.

Approximately 5 mL blood will be collected at each time point. Serum will be prepared as instructed and will be frozen within 1 hour of collection in 2 aliquots for PCSK9 and 2 aliquots for AMG 145 at -70°C (-20°C if a -70°C freezer is not available). The site will be expected to complete a shipping log or requisition that will include subject identification information and the time and date of collection for each sample shipped. Missing samples must be clearly documented on the shipping log or requisition. Please refer to the laboratory manual for detailed instructions on sample collection, processing, and shipping of PK samples.

7.4 Biomarkers Development Studies

7.4.1 Biomarker Sample Collection

Biomarkers are objectively measured and evaluated indicators of normal biologic processes, pathogenic processes, or pharmacologic responses to a therapeutic intervention.

It is expected that further advances will occur in investigational techniques that look at markers of PCSK9 signaling, LDLR turnover, cholesterol metabolism, inflammation, and plaque stability. It is not possible at this stage to anticipate what these advances will be; however, considerable benefit could accrue to future sufferers of coronary artery disease if these markers can be correlated with the data from the study. It is also important to clarify any potential drug interactions in this population of subjects who will be on a number of other drugs. For biomarker analysis, blood samples will be collected at the end of the parent study and at week 12 so that analyses may be performed that will look at markers of PCSK9 signaling, LDL-R turnover, cholesterol metabolism, inflammation, and plaque stability such as certain glycosylated proteins, matrix metalloproteinases, markers of inflammation such as C-reactive protein, myeloperoxidase, bromo and nitro-tyrosine, and Tumor Necrosis Factor (TNF) cellular adhesion molecules.

The samples collected will not be suitable for any DNA or other genetic testing and it is specifically stated that these specimens will not be used for this purpose.

Refer to the laboratory manual for detailed collection and handling procedures for all biomarker development samples.

7.4.2 Sample Storage and Destruction

The biomarker samples and any other components from the cells may be stored for up to 20 years from the end of the study to research scientific questions related to hypercholesterolemia, metabolic disorders, and/or AMG 145. The subject retains the

right to request that the sample material be destroyed at any time by contacting the principal investigator. The sponsor will be the exclusive owner of any data, discoveries, or derivative materials from the sample materials and is responsible for the destruction of the sample(s) at the request of the subject through the principal investigator or at the end of the storage period or as appropriate (eg, the scientific rationale for experimentation with a certain sample type no longer justifies keeping the sample). Following the request from the subject, the principal investigator will provide the sponsor with the required study and subject numbers so that any remaining plasma and blood samples and any other components from the cells can be located and destroyed. If a commercial product is developed from this research project, the sponsor will own the commercial product. The subject will have no commercial rights to such product and will have no commercial rights to the data, information, discoveries, or derivative materials gained or produced from the sample. See [Section 11.3](#) for subject confidentiality.

8. REMOVAL AND REPLACEMENT OF SUBJECTS

8.1 Removal of Subjects

Subjects have the right to withdraw fully or partially from the study at any time and for any reason without prejudice to his or her future medical care by the physician or at the institution.

Withdrawal of full consent for a study means that the subject does not wish to receive further investigational treatment and does not wish to or is unable to continue further study participation including any follow-up in person, by phone, through 3rd parties including relatives or friends, via discussion with other treating physicians, and by use of medical records; subject data up to withdrawal of full consent will be included in the analysis of the study. Any subject may withdraw full consent to participate in the study at any time during the study. The investigator will discuss with the subject appropriate procedures for withdrawal from the study. The investigator should ask the subject's consent to perform the procedures listed under the final study visit.

Subjects may decline to continue receiving IP or other protocol-required procedures at any time during the study. If this occurs, the investigator will discuss with the subject appropriate procedures for discontinuation from IP or other protocol-required procedures and should encourage the subject to continue with collection of data, including endpoints and adverse events. These subjects, as well as those who have stopped receiving IP or other protocol-required procedures for other reasons (eg, investigator or sponsor concern) should continue the schedule of study observations. If the subject is unable or

unwilling to continue the schedule of observation, the investigators should clarify what type of follow-up the subject is agreeable to: in person, by phone/mail, through family/friends, in correspondence/communication with other physicians, and/or from review of the medical records.

Should a subject (or a legally acceptable representative) request or decide to withdraw from the study, all efforts will be made to complete and report the observations as thoroughly as possible up to the date of withdrawal. All information should be reported on the applicable eCRFs.

Reasons for removal from protocol-required investigational product might include:

- withdrawal of full consent
- subject request to end investigational product administration
- administrative decision by Amgen
- decision by the primary investigator / physician
- pregnancy in a female subject (report on Pregnancy Notification Worksheet; see [Appendix D](#))
- adverse event

8.2 Replacement of Subjects

There will be no replacement of subjects.

9. SAFETY DATA COLLECTION, RECORDING, AND REPORTING

9.1 Adverse Events

9.1.1 Definition of Adverse Events

An adverse event is defined as any untoward medical occurrence in a clinical trial subject. The event does not necessarily have a causal relationship with study treatment. The investigator is responsible for ensuring that any adverse events observed by the investigator or reported by the subject are recorded in the subject's medical record.

The definition of adverse events includes worsening of a pre-existing medical condition. Worsening indicates that the pre-existing medical condition (eg, diabetes, migraine headaches, gout) has increased in severity, frequency, and/or duration, and/or has an association with a significantly worse outcome. A pre-existing condition that has not worsened during the study or involves an intervention such as elective cosmetic surgery or a medical procedure while on study, is not considered an adverse event.

An adverse device effect (ADE) is any adverse event related to the use of a medical device. Adverse device effects include adverse events resulting from insufficient or inadequate instructions for use, adverse events resulting from any malfunction of the

device, or adverse events resulting from use error or from intentional misuse of the device.

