9.2 Serious Adverse Events

9.2.1 Definition of Serious Adverse Events

A serious adverse event (SAE) is defined as an adverse event that meets at least 1 of the following serious criteria:

- fatal
- life threatening (places the subject at immediate risk of death)
- requires in-patient hospitalization or prolongation of existing hospitalization
- results in persistent or significant disability/incapacity
- congenital anomaly/birth defect
- other medically important serious event

An adverse event would meet the criterion of "requires hospitalization", if the event necessitated an admission to a health care facility (eg, overnight stay).

If an investigator considers an event to be clinically important, but it does not meet any of the serious criteria, the event could be classified as a serious adverse event under the criterion of "other medically important serious event". Examples of such events could include allergic bronchospasm, convulsions, blood dyscrasias, drug-induced liver injury (see [Appendix B](#)) for drug-induced liver injury reporting criteria, or events that necessitate an emergency room visit, outpatient surgery, or urgent intervention.

If adverse events correspond to Grade 4 "life threatening" CTCAE grading scale criteria (eg, laboratory abnormality reported as grade 4 without manifestation of life threatening status), it will be left to the investigator's judgment to also report these abnormalities as

serious adverse events. For any adverse event that applies to this situation, comprehensive documentation of the event's severity status must be recorded in the subject's medical record.

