10. STATISTICAL CONSIDERATIONS

10.1 Study Endpoints, Subsets, and Covariates

10.1.1 Primary Endpoint

Subject incidence of treatment emergent adverse events

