10.1.3 Exploratory Endpoints

- Subject incidence of adjudicated events
 - death by any cause
 - cardiovascular death
 - myocardial infarction
 - hospitalization for unstable angina
 - coronary revascularization
 - stroke
 - transient ischemic attack (TIA)
 - hospitalization for heart failure
- Subject incidence of non-coronary revascularization

Lipid and other efficacy laboratory parameters:

- Percent change from baseline at each scheduled visit in
 - Total cholesterol
 - VLDL-C
 - HDL-C
 - ApoA1
 - Triglycerides

- Change from baseline at each scheduled visit in the following parameters:
 - LDL-C
 - Total cholesterol
 - non-HDL-C
 - ApoB
 - Total cholesterol/HDL-C ratio
 - ApoB/ApoA1 ratio
 - VLDL-C
 - HDL-C
 - ApoA1
 - Triglycerides
 - Lp(a)
 - PCSK9

Pharmacokinetics Endpoints

- Serum concentration of AMG 145 and PCSK9 at selected time points

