2. SUBJECT INFORMATION																	
Subject ID Number			Date of Birth Day Month Year			Sex  F  M		Race									
3. SERIOUS ADVERSE EVENT - Information in this section must also be entered on the Serious Adverse Event Summary CRF																	
Provide the date the Investigator became aware of this Serious Adverse Event Information: Day Month Year																	
Serious Adverse Event Diagnosis or Syndrome If diagnosis is unknown, enter Signs / Symptoms When Final Diagnosis is known, enter as Adverse Event List one event per line. If event is fatal, enter the Cause of Death. Entry of "Death" is not acceptable, as this is an outcome.	Date Started Day Month Year	Date Ended Day Month Year	Potential Endpoint?	Check only if event occurred before first dose of IP	Enter Serious Criteria code (see codes below)	Is there a reasonable possibility that the event may have been caused by if yes see section 10				Outcome of Event 01 Resolved 02 Resolving 03 Not resolved 04 Fatal	Check only if event is related to study procedure eg biopsy						
						evolocumab (AMG 145)	Pre-filled autoinjector /pen (Allpen)	3.5 mL personal injector									
Serious Criteria:			01 Fatal		02 Immediately life-threatening		03 Required hospitalization		04 Prolonged hospitalization		05 Persistent or significant disability /incapacity		06 Congenital anomaly / birth defect		07 Other significant medical hazard		

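### Read literally, the closing sentence of the adverse event definition excludes a worsened pre-existing condition once it is managed by a procedure, which the sentences before it count as an adverse event

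*Protocol*

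**What the plan says.** Protocol 9.1.1 opens with a broad definition: any untoward medical occurrence, whether or not caused by treatment. It then states: "The definition of adverse events includes worsening of a pre-existing medical condition". Worsening means that the condition "has increased in severity, frequency, and/or duration, and/or has an association with a significantly worse outcome". Neither sentence makes an exception for conditions treated by a procedure.

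The closing sentence of the same paragraph sets out what is not an adverse event. Its first limb is "A pre-existing condition that has not worsened during the study". Its second limb continues "or involves an intervention such as elective cosmetic surgery or a medical procedure while on study, is not considered an adverse event".

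Three other places depend on this definition or bear on it:

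- Protocol 10.1.1 gives the primary endpoint: "Subject incidence of treatment emergent adverse events". Protocol 10.4.2.1 and SAP 10.5.1 tabulate these events, and the serious ones, by system organ class and preferred term.
- Protocol 9.2.1 defines a serious adverse event as an adverse event that meets a seriousness criterion. Among its examples of medically important events it names "events that necessitate an emergency room visit, outpatient surgery, or urgent intervention".
- Protocol 10.1.3 and 10.4.2.4 make coronary revascularization a CEC-adjudicated exploratory endpoint. They have non-coronary revascularization collected on the eCRF and summarized.

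**The concern.** In the second limb, the 'not' of the first limb no longer applies, because it governs only the word 'worsened'. 'Elective' describes only cosmetic surgery, so a medical procedure of any kind qualifies. Taken at its word, the sentence removes every pre-existing condition that involves a procedure on study, including one that has worsened.

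This matters in this population. Protocol 2.1 describes patients who are highly exposed to severe atherosclerotic disease. Inclusion criterion 4.1.4 provides for subjects with diagnosed coronary disease, peripheral arterial disease, aortic aneurysm and carotid disease. Progression of such disease is often managed by a procedure. If a site omits the worsened condition for that reason, cardiac and vascular rows and the serious-event tables come out too low. Any such omission can only lower the counts, and the study has no control group against which a low count would stand out.

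**Working it through.** **Step 1: the four cases under 9.1.1.**

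| Pre-existing condition | Procedure on study | Earlier sentences | Closing sentence, literal | Closing sentence, likely intent |
|---|---|---|---|---|
| Not worsened | No | Not an AE | Not an AE | Not an AE |
| Not worsened | Yes | Not an AE | Not an AE | Not an AE |
| Worsened | No | AE | Not excluded, so AE | AE |
| Worsened | Yes | AE | **Not an AE** | AE |

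The conflict lies in the last row only.

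**Step 2: does another section settle that row?** Protocol 9.2.1 starts from an adverse event, so an occurrence excluded in 9.1.1 cannot become serious by that definition. Its examples of outpatient surgery and urgent intervention lean toward reporting but do not limit the exclusion. The SAP 6.3 definition of a treatment-emergent event is a timing rule for events already entered on the eCRF. It says nothing about procedures. No section limits the second limb.

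**Step 3: the plan's own precision figure.** Protocol 10.2 gives 95% intervals for a particular adverse event at about 5%. With p ± 1.96 × √(p(1−p)/n):

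- 15/300: 0.0253 to 0.0747 (plan: 0.03, 0.07)
- 16/310: 0.0270 to 0.0762 (plan: 0.03, 0.08)
- 16/320: 0.0261 to 0.0739 (plan: 0.03, 0.07)

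The table reproduces and is not in dispute. It serves below only as a scale.

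**Step 4: effect on a single preferred term (illustration).** The share unreported is assumed. For a term truly present in 16/310 = 5.2%:

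- 25% unreported: 12/310 = 3.9% (95% interval 1.7% to 6.0%)
- 50% unreported: 8/310 = 2.6% (0.8% to 4.3%)

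**Step 5: effect on the share with any treatment-emergent event (illustration).** A subject is lost from this count only if the omitted event was the only one. Let a be the share of subjects with an omitted event and q the share with another treatment-emergent event. If the two are independent, the loss is a × (1 − q).

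- a = 2%, q = 95%: 0.02 × 0.05 = 0.1 points
- a = 10%, q = 80%: 0.10 × 0.20 = 2.0 points
- a = 2% to 10%, q = 57%: 0.02 × 0.43 = 0.9 to 0.10 × 0.43 = 4.3 points

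The 57% is the incidence on AMG 145 in the completed phase 2 studies (Protocol 2.2.4.4), which lasted 12 weeks (2.2.3). Over 260 weeks q should be higher, so the first two lines are the more relevant.

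**The case against.** The best defence is that the closing sentence has a natural narrower meaning. The paragraph has just said, without exception, that worsening is an adverse event. The remainder then reads as covering conditions that have not worsened, including those with an incidental procedure, and the cosmetic-surgery example points to elective work. Many investigators will read it so. A myocardial infarction, or another new acute event, is an untoward occurrence in its own right and need not fall under an exclusion about pre-existing conditions. Protocol 9.1.2 also asks for the diagnosis or syndrome, and 9.2.1 leans toward reporting.

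Most of this stands as an account of intent. It does not remove the conflict, because a site must set the literal wording aside to reach that intent.

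Three stronger readings are tempting, and the documents do not support them:

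- A reader might infer that revascularizations are lost to adjudication, because "Potential Endpoint" is a column on the sample serious adverse event form in Appendix C. Nothing says that this form is the only route to the CEC. Protocol 10.4.2.4 already requires adjudication of coronary revascularization and eCRF collection of non-coronary revascularization.
- A reader might attach assumed disease prevalence and procedure rates to the 310 subjects and compare the total with the 16/310 row. The documents give neither rate. That row shows precision for one particular event, not for the overall endpoint.
- A reader might infer that sites do apply the exclusion literally. No document shows this.

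**Conclusion.** The contradiction in 9.1.1 is real on the wording, is confined to worsened conditions managed by a procedure, and is not resolved elsewhere. It should be corrected because it sits in the definition behind the primary endpoint.

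The exposure is in cardiac and vascular preferred terms and in serious treatment-emergent events. For a single term, the loss is proportional to the share unreported, which is unknown. The overall proportion with any treatment-emergent event would hardly move: about 0.1 to 2.0 points, on the assumptions that 2-10% of subjects are affected, that 80-95% have another event, and that the two are independent. Whether any loss occurs depends on how sites read the sentence. The procedures of most interest, revascularizations, remain in the data as exploratory endpoints.

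**What to change.** Reconcile the sentences in Protocol 9.1.1 so that the procedure limb applies only to conditions that have not worsened. Suggested wording:

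*A pre-existing condition that has not worsened is not an adverse event, even if an elective or pre-planned procedure for it takes place on study. If a procedure is done because a condition is new or has worsened, the underlying condition is recorded as an adverse event, and as a serious adverse event if 9.2.1 is met.*

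Notify sites of the clarification. Before database lock, cross-check the revascularizations collected under 10.4.2.4 against the adverse event data, and query any without a matching event. A mismatch is a reason to query, not proof of an omission, since a planned procedure for stable disease is properly not an adverse event. The check will not find worsened conditions managed by other kinds of procedure. No new rule for capturing revascularizations is needed, because 10.4.2.4 already provides for it.

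The cost is a short protocol change, a site notification, some queries and slightly more adverse event and serious adverse event entries. Sample size, visits and planned tables are unchanged.
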